6.2.3. Sensitivity Analyses

Sensitivity analysis 1: This analysis will be performed by imputing missing ACT values using the multiple imputation (MI) method assuming missing at random (MAR). Those who discontinue the treatment before Week 24 due to technology failure, disliking the digital platform, adverse event related to IMP, or disliking the IMP will be considered having missing data. For those who discontinue early not due to these reasons, the ACT value assessed at the ET visit will be used. Those who discontinue early and do not have an ET visit will be considered having missing data.

The following steps will be performed for the analysis:

- Create complete datasets using imputation. The SAS code is as follows:

```
proc mi data = yy out = yy2 seed = 4192 n impute = 500 minimum = 5 maximum = 25;  
  class trt;  
  var trt actbase v2 v3;  
  monotone regpmm;  
run;
```
- For each dataset, the clinically important improvement in asthma control variable will be derived for each patient as defined in Section 6.2.1.
- Analyze each dataset using the model described below for the primary endpoint.

```
ods output Diffs = dif LSMeans = lsm;  
proc genmod data = indata;  
  by visit_imputation_;  
  class trt;  
  model y = trt actbase / dist = binomial;  
  lsmeans trt/pdiff cl diff exp;  
run;  
ods output close;
```

- The output datasets from the above analysis will contain odds ratio estimates from each of the 500 datasets. An overall estimate will be generated using PROC MIANALYZE . The SAS code is as following:

```
proc mianalyze data=zz;
  by visit;
  modeleffects estimate;
  stderr stderr;
  ods output paramestimates=or;
run;
```

Sensitivity analysis 2: The primary variable will be analyzed using the same method as defined in Section 6.2.2 excluding the random site effect from the logistic model. The SAS code will be used for the analysis:

```
proc mcmc data = x nbi = 1000 nmc = 500000 thin = 20 seed = 159 outpost =
post2 monitor = (beta0-beta2 sigma2 pi pi0 pooled or) statistics=(summary
intervals);

parms beta0-beta2 0;
prior beta0 ~ normal (mean = -0.231, var = 0.192);
prior beta1 ~ normal (mean = 0.236, var = 9.912);
prior beta2 ~ normal (mean = 0, var = 1000);
eta = beta0 + beta1*trt + beta2*y0;
pi = logistic(eta);
pi0 = logistic(beta0 + beta2*y0);
model count ~ binomial(n = total, p = pi);
pooled = exp(beta1);

run;
```

where count = number of responders and total = number of patients.

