6.1. Assessments of Patient-Reported Outcomes

6.1.1. Asthma Control Test

The ACT is a simple, patient-completed tool used for the assessment of overall asthma control. The 5 items included in the ACT assess daytime and nighttime asthma symptoms, use of rescue medication, and impact of asthma on daily functioning. Each item in the ACT is scored on a 5-point scale, with summation of all items providing scores ranging from 5 to 25. The scores span the continuum of poor control of asthma (score of 5) to complete control of asthma (score of 25), with a cutoff score of 19 and below indicating patients with poorly controlled asthma (Schatz et al 2006).

The ACT should be the 1st questionnaire completed by all patients during a study visit (followed by the Mini-AQLQ, WPAI questionnaire, BMQ, and then the BIPQ, respectively, all completed by patients 18 years of age or older, and should precede any discussion between the patient and investigational center personnel. The self-administered version of the ACT will be answered by the patients at Visit 1, Visit 2, Visit 3, or at the ET visit. For Visit 1, Visit 3, or the ET visit, the ACT will be administered in person at the investigational center. For Visit 2, the ACT may be administered by telephone. The investigators and personnel will be provided with detailed instructions for administering the ACT in order to achieve maximum compliance in a clinical study environment (or by telephone) and maximum data quality. Caregivers or investigational center personnel will not be allowed to interfere or communicate with the patient completing the questionnaire beyond restating the question(s) on the questionnaire exactly as they have been written. After completion of the ACT, investigational center personnel will check the questionnaires for completeness and legibility. Detailed instructions for administering, scoring, and analyzing the ACT are provided in the Statistical Analysis Plan.

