2.4. Sample Size and Power Considerations

The sample size was selected based on a Bayesian approach which allows for a range of underlying proportions rather than a fixed predefined value.

A total of 388 patients will be enrolled in the study (accounting for 10% early dropouts), 200 patients in the DS group and 150 patients in the SoC group, to be available for analysis. The sample size determination was made assuming binomial distribution for the primary endpoint. An informative prior for the SoC group (Beta [9.52, 11.88]) was selected to reflect the belief that the response rate of the SoC group is between 30% and 60% (most likely 45%, [Merchant 2016](#)) and the effect size between groups of 13% difference in response rates was considered clinically meaningful.

In addition, an informative prior for the SoC group was selected to ensure that the mean square error for the Bayes estimate from the informative prior is superior to the maximum likelihood estimate over a range of 30% and 60% of anticipated proportion for SoC group.

It should be noted that both power and Type 1 error are dependent on the absolute difference between the DS and the SoC groups as illustrated in [Figure 1](#) below by the operational characteristics calculated for the study design.

Figure 1: Operational Characteristics Calculated for the Study Design

MSE=maximum likelihood estimation; MSE=mean squared error

A non-informative prior (Beta [0.5,0.5]) for the DS group was selected due to lack of availability of data in the DS group.

With assumptions of response rates of 58% and 45% for the DS and SoC groups, respectively, sample size and randomization ratio, the probability of the posterior odds ratio (OR) of improvement (ie, $OR > 1$) for the DS group versus the SoC group of at least 0.95 is about 82%. This will ensure a 1-sided 5% Type 1 error rate and 78% power for an effect size for 13% difference between the groups provided that the proportion of responders in the SoC group is 45%.

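### Sensitivity analysis 1 uses a monotone imputation routine on data that need not be monotone, and sets aside the early-termination ACT of some leavers for whom it is usually the only postbaseline score

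*SAP*

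**What the plan says.** SAP 6.2.3 describes sensitivity analysis 1 as multiple imputation of ACT under missing at random (MAR).

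- **Listed reasons.** Patients who stop before Week 24 for technology failure, disliking the digital platform, "adverse event related to IMP, or disliking the IMP will be considered having missing data". No exception is made for a patient with an ET score.
- **Other reasons.** "For those who discontinue early not due to these reasons, the ACT value assessed at the ET visit will be used". Leavers without an ET visit are missing.
- **Imputation model.** The variables are "var trt actbase v2 v3" and the routine is "monotone regpmm". There is no ET variable, no reason for leaving, and no earlier step that makes the pattern monotone.
- **Collection.** Protocol 6.1.1: "The self-administered version of the ACT will be answered by the patients at Visit 1, Visit 2, Visit 3, or at the ET visit". Protocol 4.3 asks for the end-of-treatment assessments at early termination where possible.
- **Analysis set.** SAP 3.1.2 requires at least one postbaseline ACT for the mITT set.
- **Primary rule.** SAP 6.2.2 counts the listed-reason leavers as nonresponders.
- **Section 11.** It says that leavers with an IMP-related adverse event are nonresponders in the sensitivity analyses too, and points to 6.2.3, which instead makes them missing.

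**The concern.** There are two separate problems.

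The first is a mismatch between code and data. A monotone routine imputes each variable from those before it in the list, so it presupposes that once a value is missing all later ones are missing. The rules in 6.2.3 and ordinary missed visits both produce the opposite: v2 absent, v3 present.

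The second is unused data. A patient who leaves before Week 12 for a listed reason has not reached Visit 2, so the ET score is normally the only evidence of how that patient fared. Setting it aside leaves arm and baseline as the only predictors. MAR is then harder to defend, because the imputation ignores an observed variable that may well be related both to leaving and to Week 24 control. Technology failure and disliking the platform can occur only in the DS arm, so any resulting shift is likely to fall mainly on DS. Sensitivity analysis 2 only removes the centre effect, which leaves this as the plan's one sensitivity analysis of missing data.

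**Working it through.** **1. The plan's own figures.** The documents give no figure for sensitivity analysis 1. The design figures that set the scale do reproduce. From "With assumptions of response rates of 58% and 45% for the DS and SoC groups, respectively", with 200 and 150 patients and one-sided 5%:

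- pooled rate = (200 × 0.58 + 150 × 0.45)/350 = 0.524
- SE under no difference = √(0.524 × 0.476 × (1/200 + 1/150)) = 0.0539
- SE under the alternative = √(0.58 × 0.42/200 + 0.45 × 0.55/150) = 0.0536
- power = Φ((0.13 − 1.645 × 0.0539)/0.0536) = Φ(0.77) = 0.78, as stated

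Exact enumeration with the two Beta priors gives 0.817 against the stated 82%. Enrolment is 350/0.90 = 388.9 against 388. The point does not depend on these.

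**2. Which patients break the monotone pattern.**

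| Patient | v2 | v3 | Monotone? |
|---|---|---|---|
| Completer, both visits | present | present | yes |
| Completer, Visit 2 missed | missing | present | no |
| Other-reason leaver before Week 12, ET score used | missing | ET score, if held in v3 | no |
| Listed-reason leaver before Week 12 | missing | set to missing | yes |
| Listed-reason leaver after Visit 2 | present | set to missing | yes |

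Row 3 rests on an inference. The SAP does not say that the ET score goes into v3. If it does not, the rule that it is used cannot be carried out with this code, which has no other place for it. Row 2 needs no inference.

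One such patient is enough. The plan allows for 388 − 350 = 38 dropouts. The shares below are assumptions:

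- 5% of dropouts fit row 3: 1 − 0.95^38 = 86% chance of at least one
- 10% fit row 3: 1 − 0.90^38 = 98%
- 1% of 350 completers miss Visit 2: 1 − 0.99^350 = 97%

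**3. What is left to predict Week 24.** The ACT is scheduled at Visits 1, 2 and 3 or ET. A patient who leaves before Week 12 therefore normally enters the mITT set through the ET score, which 6.2.3 then blanks for the listed reasons. A listed-reason leaver with a Visit 2 score is different: v2 is in the model and is used.

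**4. Size, under assumptions.** Let d be the share of the DS arm leaving for listed reasons, e the fraction of them leaving before Week 12, and g the gap between imputed and true Week 24 response in those early leavers. If later leavers are imputed well from v2,

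shift in DS rate ≈ d × e × g.

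A simulation of 222 DS patients (baseline ACT 14, SD 2.8, capped at 18; early change 2.5, SD 3; leaving more likely after a poor early change) gave leavers a true response of 38.8% and an imputed response of 64.4%, so g = 25.6 points.

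- d = 10%, e = 1: 0.10 × 25.6 = 2.6 points
- d = 5%, e = 0.5: 0.05 × 0.5 × 25.6 = 0.6 (a separate simulation gave 0.7)
- d = 2%, e = 0.5: 0.02 × 0.5 × 25.6 = 0.3
- leaving unrelated to early ACT: g ≈ 0, so about 0

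A second simulation used 388 patients, matching on arm, baseline and v2, 5% other-reason leavers and half of all leavers before Week 12. It compared the coded analysis with using the ET score as final for every leaver:

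| d | ET response in leavers | Imputed response | DS rate, ET used | DS rate, as coded | Difference (points) |
|---|---|---|---|---|---|
| 2% | 29.7% | 58.3% | 60.4% | 60.9% | 0.5 |
| 2% | 8.1% | 48.4% | 58.5% | 59.3% | 0.8 |
| 5% | 27.4% | 53.6% | 59.1% | 60.5% | 1.4 |
| 5% | 7.6% | 49.5% | 57.5% | 59.6% | 2.1 |
| 10% | 29.6% | 56.2% | 57.9% | 60.6% | 2.7 |
| 10% | 9.7% | 47.8% | 55.1% | 58.9% | 3.8 |

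About 9 of the 388 simulated patients had the row 3 pattern.

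**The case against.** The strongest defence is that the imputation answers a legitimate question. The primary analysis already gives listed-reason leavers the least favourable value. Sensitivity analysis 1 asks what would have happened had they stayed, and an ET score is not a Week 24 score. That stands as a reason to impute. It does not explain leaving the only postbaseline score out of the model.

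The size is also easy to overstate, and these objections stand:

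- The documents' 10% is dropout for all reasons in both arms. A reader might infer a bias of about one fifth of the 13-point planned effect (2.6/13). That requires 10% of the DS arm to leave for listed reasons, all before Week 12 and after poor early change. None of this is in the documents.
- A technology failure may have nothing to do with early control, in which case the shift is near zero.
- A reader might infer that all such leavers are imputed as if they were completers. Those with a Visit 2 score are imputed from it, and the donors include other-reason leavers if their ET scores sit in v3.
- A reader might infer that the listed reasons are peculiar to DS. Only two of the four are. SoC medication counts as IMP in SAP 3.1.2, so IMP-related adverse events and disliking the IMP can arise in either arm.
- It does not follow that the code would be rewritten after the data are seen. SAP 2.5.2 provides for amendments approved before database lock.

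**Conclusion.** The concern holds as two limited defects in SAP 6.2.3. The monotone routine does not fit patterns that the plan allows and that are very likely to occur; the missed-Visit-2 route alone establishes this. The analysis also sets aside the ET score of listed-reason leavers, which for those leaving before Week 12 is usually their only postbaseline ACT. That weakens MAR and, if such leavers did worse early, moves the DS rate upward.

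The documents do not fix the amount. With 2% to 10% of the DS arm assumed to leave for these reasons, it runs from about 0, when leaving is unrelated to early ACT, to roughly 2.5 to 4 points at the extreme. The top of that range, 3.8, takes the ET score as the truth for every leaver and assumes ET response near 10%.

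A reader might go further and infer that the trial's conclusion is biased towards DS. The documents do not support that: the primary analysis counts these patients as nonresponders, and no decision rule is attached to this sensitivity analysis. Separately, 6.2.3 and Section 11 contradict each other on IMP-related adverse events. Both are in the SAP, so its precedence over the protocol does not settle the matter.

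**What to change.** Amend SAP 6.2.3 before database lock:

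1. Replace `monotone regpmm` with `fcs regpmm`, or first impute the gaps that break the pattern and then keep the monotone step.
2. For listed-reason leavers before Week 12, enter the observed ET ACT in the v2 position, so that only Week 24 is imputed.
3. Leave later listed-reason leavers to be imputed from their observed v2. Do not add a separate ET variable: completers have no ET score, so its relation to Week 24 could not be estimated.
4. State which variable holds the ET score of other-reason leavers.
5. Decide whether IMP-related adverse event leavers are nonresponders or missing in this analysis, and word 6.2.3 and Section 11 alike.

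The cost is a few lines of code and two or three sentences. An ET score then stands in for a Week 12 score, which is an approximation, and the DS result in this sensitivity analysis may be slightly less favourable. The primary analysis does not change.

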6.2.4. Supplementary Analysis

A supplementary analysis for the proportion of patients for the DS and SoC groups reaching well-controlled asthma as defined by an ACT score of greater than or equal to 20, or a clinically important improvement in asthma control as defined by an increase of at least 3 units on the ACT score from baseline at the end of 12-weeks during the treatment period (responder analysis of DS versus SoC group with responders defined by an ACT score of greater than or equal to 20 or an increase by greater than or equal to 3 units on the ACT score) will also be performed using the same analysis method as defined for the primary endpoint (see Section 6.2.2).

6.3. Secondary Endpoints and Analysis

6.3.1. Secondary Endpoint #1 – Frequency and Types of Interventions Done to Improve Asthma Control

6.3.1.1. Definition

Secondary endpoint #1 will describe the frequency and types of interventions done to improve asthma control including:

- number of discussions between patient and HCP regarding inhaler technique or adherence
- number of adjustments of therapy including:
 - increased or decreased doses of inhaled medication
 - change to different inhaled medication
 - additional inhaled medication
 - addition of a systemic corticosteroid medication for asthma or another controller, including a LAMA or biologics
- frequency of intervention to manage comorbid conditions associated with poor asthma control (GERD, sinusitis, etc.)

6.3.1.2. Analysis

Frequency and types of interventions during the 24-week treatment period will be summarized as count data using descriptive statistics. In addition, similar Bayesian analysis specified for primary endpoint will be performed for those variables separately using Poisson regression. The suggested SAS code for the analyses is as follows:

```
proc mcmc data = x nbi = 1000 nmc = 100000 thin = 20 seed = 159 outpost = post3
  monitor = (beta0-beta3 sigma2 lambda lambda0 pooled) statistics=(summary intervals);
  parms beta0-beta3 0;
  parms sigma2 1;
  prior beta0-beta3 ~ normal(mean = 0, var = 1000);
  prior sigma2 ~ igamma(shape = 0.001, scale = 0.001);
  random b0 ~ normal(mean = 0, var = sigma2) subject = CENTER;
  eta = beta0 + b0 + beta1*trt + beta2*logt + beta3*y0;
  lambda = exp(eta);
  lambda0 = exp(beta0 + b0 + beta2*logt + beta3*y0);
  model hosp ~ poisson(lambda);
  array lmda[<# of sites>];
  lmda[CENTER] = exp(b0 + beta1 + beta2*logt + beta3*y0);
  pooled = exp(beta1);
run;
```

6.3.2. Secondary Endpoint #2 – Evaluation of Short-Acting Beta₂ Agonists Usage**6.3.2.1. Definition**

Secondary endpoint #2 is the change from week 1 in the mean weekly SABA usage and the change from week 1 in the number of SABA-free days over the 24-week treatment period for the DS group. SABA usage and SABA-free days. Weekly average SABA use will be defined as ((number of inhalations in a week)*90 ug/7) and change from week 1 in weekly average SABA use will be defined as (week i – week 1). Weekly SABA-free days will be defined as number of days a patient does not use the rescue medication in a week. If no inhalations done for any week, the amount of the SABA use will be 0 and SABA-free days for week will be 7.

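### The suggested Poisson model for secondary endpoint #1 has no patient-level dispersion term, so its interval for the treatment ratio will be too narrow if counts vary more than Poisson within centre

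*SAP*

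**What the plan says.** SAP 6.3.1.2 starts with a descriptive analysis: "Frequency and types of interventions during the 24-week treatment period will be summarized as count data using descriptive statistics". It then adds that a "similar Bayesian analysis specified for primary endpoint will be performed for those variables separately using Poisson regression", introduced by "The suggested SAS code for the analyses is as follows".

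The code has these parts:
- Linear predictor: "eta = beta0 + b0 + beta1*trt + beta2*logt + beta3*y0".
- Likelihood: "model hosp ~ poisson(lambda", a plain Poisson.
- Only random term: "random b0 ~ normal(mean = 0, var = sigma2) subject = CENTER".
- Priors: "prior beta0-beta3 ~ normal(mean = 0, var = 1000". The logt coefficient is therefore estimated and not held at 1.
- Treatment summary: "pooled = exp(beta1".

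The section has no negative binomial likelihood, patient-level random effect, scale parameter or dispersion check, and it does not define logt or y0. SAP section 7 names the primary endpoint and secondary endpoint #1 as the ones with Bayesian methods. All other endpoints are descriptive.

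**The concern.** Given centre, treatment, logt and y0, the model sets the variance of each count equal to its mean. The centre intercept absorbs differences between centres. Randomisation is stratified by centre (SAP 2.2), so the treatment contrast is made largely within centres, and its error comes from variation between patients within a centre. The centre term cannot absorb that.

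The trial's design makes extra variation plausible. Interventions are recorded at Visits 2 and 3 and at Clinically Driven Assessments. The latter are unscheduled and held at the patient's request or the investigator's discretion (Protocol 3.1 and Appendix B), and no clinical decisions are mandated. Some patients may generate many contacts and others none. Counts of repeatable actions, such as discussions and dose changes, are the most exposed.

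What is at stake is the interval for the only secondary endpoint with a modelled comparison between arms. If it is too narrow, differences in intervention frequency will look more precisely estimated than they are.

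**Working it through.** **The plan's own figure.** None exists. The documents give no expected count, variance or precision target for this endpoint.

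**Inputs from the documents.** 200 DS and 150 SoC patients and 10% early dropout (SAP 2.4); 4:3 allocation stratified by centre (SAP 2.2); about 45 centres (Protocol 3.2); no data after early discontinuation (SAP 6.2.2).

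**Assumptions not in the documents.** Mean count 2 per patient (0.5 and 4 as side checks); residual variance-to-mean ratio φ from 1 to 3; centre SD 0 or 0.4 on the log scale; dropout uniform over weeks 2 to 24; true rate ratio 1.

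**Step 1: SD that the Poisson model reports.** Ignoring dropout and centres, Var(log ratio) ≈ 1/(200×2) + 1/(150×2) = 0.0025 + 0.0033 = 0.0058, so SD ≈ 0.076. Simulation of the SAP model gives 0.079 to 0.080.

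**Step 2: actual SD and coverage.** With ratio φ the actual SD is about √φ times the reported one, so coverage ≈ 2Φ(1.96/√φ) − 1, where Φ is the standard normal distribution function:
- φ = 1.5: 1.96/1.225 = 1.600, coverage 89.0%
- φ = 2: 1.96/1.414 = 1.386, coverage 83.4%
- φ = 3: 1.96/1.732 = 1.132, coverage 74.2%

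**Step 3: simulation.** The SAP model was fitted with random centre intercept and N(0, 1000) priors, using a Laplace approximation in place of PROC MCMC (2000 runs per row). The last column is a simpler Poisson regression on simulated counts (800 runs, early leavers uniform over weeks 2 to 22).

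| φ | Reported SD | Actual SD | Ratio | Coverage, SAP model | Coverage, simpler model |
|---|---|---|---|---|---|
| 1 | 0.0793 | 0.0807 | 1.02 | 94.7% | not run |
| 1.5 | 0.0795 | 0.0998 | 1.26 | 88.5% | 89% |
| 2 | 0.0796 | 0.1149 | 1.44 | 82.7% | 84% |
| 3 | 0.0797 | 0.1474 | 1.85 | 70.6% | 75% |

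The loss depends little on the mean count. At φ = 2, coverage is 81.4% for a mean of 0.5 and 82.0% for a mean of 4.

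**Step 4: negative binomial likelihood.** At φ = 2 and mean 2, the posterior SD is 0.114 against an actual SD of 0.111, and coverage is 94.7%. With 150 runs, the Monte Carlo standard error is √(0.947×0.053/150) = 1.8 points. The SD rises by 0.1139/0.0796 − 1 = 43%. For an estimated ratio of 1, the interval goes from exp(±1.96×0.0796) = 0.86 to 1.17, to exp(±1.96×0.1139) = 0.80 to 1.25.

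**Step 5: logt, checked separately.** Replacing the free coefficient by an offset, with nothing else changed, at φ = 2: SD 0.0796 either way, coverage 82.7% free and 82.5% offset, bias about 0 in both. What the free coefficient does change is the scaling of expected counts, which go as t^beta2. Its posterior SD is about 0.27 (0.84 if only 2% drop out). For a patient followed for half the period, beta2 = 1 ± 0.27 gives an expected count of 0.5^1.27 = 0.42 to 0.5^0.73 = 0.60 of the full-period count.

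**The case against.** The strongest reply is that overdispersion is assumed and not shown. The model already conditions on centre and y0. If y0 is baseline ACT, as in the parallel primary-analysis code, part of the clustering by poor control is adjusted for. The intervention types are modelled separately, so several types arising at one contact do not by themselves overdisperse any one count. Scheduled visits make some counts more regular, and a type that is almost always 0 or 1 cannot be much overdispersed. All of this stands, and it makes the conclusion conditional. It does not show that the remaining variance equals the mean, and the plan has no check for it.

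The reply on importance also stands. The objective is to describe, descriptive statistics come first, and the code is labelled as suggested.

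A reader might infer more than the documents support:
- **That the free logt coefficient narrows the intervals.** Step 5 shows no effect on exp(beta1) or its interval. Differential dropout by arm was not examined.
- **That the free coefficient makes the results wrong.** The endpoint is a number or frequency of interventions over the treatment period, not a promised rate per unit time, and exp(beta1) is still a ratio at equal follow-up.
- **That the trial will declare false arm differences.** No decision threshold is set for this endpoint. This model's monitor list, unlike the primary one, contains no posterior probability that beta1 exceeds zero, and SAP section 7 disclaims hypothesis testing. A false-positive rate therefore has no rule to refer to.
- **That the centre-level line, which omits beta0, corrupts a reported result.** That array is not in the monitor list.

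**Conclusion.** The point holds as a conditional and minor one. The suggested model has no protection against variation between patients within a centre. If the residual variance-to-mean ratio is 1.5, 2 or 3, nominal 95% intervals for the treatment ratio cover about 88–89%, 83–84% and 71–75%. If it is 1, they cover about 95%. The documents do not say which of these applies, so it cannot be stated that the intervals will be too narrow, only that the plan leaves this open where a standard model would not.

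The figures rest on gamma-mixed counts, the assumed means and ratios, and a Laplace approximation. The direction does not depend on the approximation, because the closed-form calculation agrees. The primary endpoint is unaffected.

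**What to change.** In the 6.3.1.2 code, replace the Poisson likelihood by a negative binomial with mean lambda and an estimated dispersion parameter. Alternatively, keep the Poisson and add to eta a normal random effect with patient as subject and its own variance. Continue to report exp(beta1).

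The cost is a few lines of code before database lock. Where overdispersion exists the intervals widen, by about 40% in posterior SD at a ratio of 2, which is the correct width. Where it does not, they are essentially unchanged.

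Three tidying changes belong in the same edit, none of which alters the treatment ratio or its interval:
- define logt and y0;
- hold the logt coefficient at 1 if lambda is to be reported as a rate per unit time, or state why it is left free;
- add beta0 to the lmda line.
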